Official title: The acute effect of instant coffee in different forms on plasma metabolites

NCT number: XXX

Document date: May 23, 2025

Study Protocol and Statistical Analysis Plan

The procedures are as follows:

1. Do not consume coffee, tea, chocolate, or other caffeinated foods and drinks for the whole day (i.e. 24hrs) before the study.
2. Take informed consent that explains what is in the capsule, what is done with the data, and the risks of a blood draw.
3. Venous fasting blood draw in the morning.
4. Ingestion of the capsule or a cup of coffee beverage after the blood draw.
5. Answer a short questionnaire (age, sex, race, education level, alcohol use, usual coffee and tea use [green, Oolong, black tea], intake of fruit, vegetables, legumes, whole grains, menopausal status, oral contraceptive use [affects caffeine metabolism])
6. Another venous blood draw after 1 hour.
7. Process and store the blood correctly.

Recruitment of study participants

Study participants (n=15) will be recruited via flyers (e.g., shopping malls, MRT stations, neighbourhood shops, community centres, food centres, tertiary institutions such as NUS), advertisements at on-campus notice boards, bus-stops and newspapers. Recruitment email within NUS will be sent by the respective administrative officers of the project team members. Recruitment will also be conducted through online platforms such as Telegram, Facebook and Instagram, as well as snowballing and convenience sampling through referrals. Participants will be screened for their eligibility over a phone call with a screening questionnaire before they are enrolled into the study.

A short screening questionnaire will be administered to each participant to obtain information on their basic demographics, lifestyle, and medical history. Inclusion criteria include individuals aged 21-64 years old and of Chinese ethnicity. Exclusion criteria include pregnancy, specific medication use including recent use of antibiotics, presence or history of diseases (e.g., cancer, cardiometabolic, endocrine), major surgical operations, depression, anxiety, caffeine intolerance, fear of needles and/or blood disorders. Written informed consent will be obtained from each participant prior to the

commencement of the study.

Briefing session and informed consent

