A briefing session will take place before the day of the study visit through an arranged Zoom/phone call. Participants who opted for a zoom call will be sent a scheduled meeting link, where he/she will be briefed by a study team member and/or PI/ Co-I. Over the call, researchers will explain the project aims and intervention study, and answer questions that the participants may have. Participants will be given or emailed handouts on foods/drinks not allowed to be consumed one day (i.e. 24hrs) before the visit (if the visit is scheduled at 8am, participants should abstain from the stated food/drinks from the day before at 8am). Participants will also be reminded to bring their medication and dietary supplements along to visit 1 for recording purposes.

Written informed consent will be obtained from each participant on the day of the first study visit. This will be performed by a study team member and should be completed within half an hour prior to the start of the study. Only participants who consent and completed the study visit(s) will be compensated. Participants will be reimbursed \$50 at the end of the second study visit. Participants who wish to withdraw after completing the first study visit will be reimbursed \$20.

Pre-study Commencement:

Before commencing the study visits, participants will be requested to fast overnight (8-12h). Drinking plain unflavoured water is allowed. Participants will be told to avoid vigorous physical activity except for activities of daily living for at least 24 hours prior to the session.

The day (24 hrs) before the study visits, participants will also be requested to avoid certain foods and beverages that may confound the study design including coffee and tea, coffee or tea-flavoured foods, caffeine-containing beverages (i.e., Coca-Cola, energy drinks), supplements containing caffeine or of herbal/botanical origin, chocolate, and chocolate-containing foods. We will communicate this over a phone call/messaging app with the participants before commencing the study, and provide a pamphlet

containing pictures and a detailed list of “allowed” and “non-allowed” foods and beverages.

Study Visit and Blood Collection:

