The 2 study visits will take place at Investigational Medicine Unit (IMU), NUS Yong Loo Lin School of Medicine, with random assignment to either coffee capsules first or coffee as a beverage first. Each participant should go through both capsule and beverage interventions. The number of participants randomised to start with the capsule will be similar to those starting with the beverage. During each visit, 12 mL of venous blood will be collected at 2 time points each – at fasting and 1 hour after the consumption of the coffee capsule/drink. During the first visit, we will also ask the participant to fill out a questionnaire about their personal characteristics (DOB, gender, education level, smoking habits, height, weight, usual [referring to the past year] consumption of coffee and tea [number of cups per day of caffeinated and decaffeinated], soft drinks with caffeine such as cola, energy drinks such as Red Bull, chocolate, and key foods in the diet such as fruits and vegetables, alcohol use, dietary supplement use, medication use, menopausal status (Annex E). The period between 2 study visits will range between 7 to 28 days.

Ingestion of coffee capsule

A single dose will be provided to participants, in the form of two capsule or one cup of coffee beverage containing 1.7 grams a commonly used commercially available instant coffee (NESCAFE Taster's Choice House Blend Coffee Stick Packs consisting of 100% coffee beans and no other ingredients). 1.7 grams of instant coffee is the amount recommended for 1 cup of instant coffee by the manufacturer. Based on our previous measurements of caffeine in this coffee (Wedick, N.M., et al. Effects of caffeinated and decaffeinated coffee on biological risk factors for type 2 diabetes: a randomized controlled trial. Nutr J 2011;10, 93) the amount of caffeine for this amount of coffee is 59 mg which is substantially lower than the amount of coffee in a standard cup of brewed coffee which typically contains 92 mg of caffeine and much lower than the maximum amount of caffeine recommended per occasion which is 200 mg (EFSA Panel on Dietetic

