precursor, which can be used for level I identification and accurate quantification in this project. A quality control extract of pooled serum from all study participants will be injected at the beginning and end of each run, and in-between every 10 samples.

Data processing and Compound identification

Quantification of the biomarker compounds will be processed using MassLynx (Waters-specific software).

Metabolite assay

1. Atractyligenin
2. Trigonelline (HCl)
3. Caffeine
4. Theobromine
5. Theophylline (1,3-Dimethylxanthine)
6. Paraxanthine (1,7-Dimethylxanthine)
7. Caffeic acid
8. 3,4-dihydroxyhydrocinnamic acid (dihydrocaffeic acid)
9. Quercetin
10. Cyclo(Pro-val)
11. Cyclo(Leu-Pro)
12. 5-Acetylamino-6-formylamino-3-methyluracil
13. 5-Acetylamino-6-amino-3-methyluracil hydrate
14. 3-CQA (Chlorogenic acid)
15. 1-methylxanthine
16. Kaempferol
17. 1-methyluric acid

18,1,7-dimethyluric acid

Statistical analysis

We will calculate mean changes in serum concentrations of biomarkers between the fasting state and after ingestion of the capsule or coffee with corresponding 95% confidence intervals. Furthermore, we will test whether changes in concentrations differ between the coffee and the capsule intervention using paired t-tests.

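### Does the capsule-versus-beverage comparison need a stated estimate and confidence interval beside the paired t-test?

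*Combined protocol and SAP*

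**What the plan says.** The Statistical analysis section of the combined protocol and SAP has two sentences. The first reads "We will calculate mean changes in serum concentrations of biomarkers between the fasting state and after ingestion of the capsule or coffee", and the text continues "with corresponding 95% confidence intervals. Furthermore, we will test whether changes in concentrations differ between the coffee and the capsule intervention using paired t-tests". So 95% intervals are tied to the changes from fasting, and the comparison of the two forms is tied to a paired t-test. No other section mentions an estimate or interval for the difference between forms.

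The design is a two-visit crossover. Under Study Visit and Blood Collection, participants attend "with random assignment to either coffee capsules first or coffee as a beverage first", and "Each participant should go through both capsule and beverage interventions". Sequence sizes are to be balanced: "The number of participants randomised to start with the capsule will be similar to those starting with the beverage". The sample size is given under Recruitment of study participants ("Study participants (n=15) will be recruited via flyers") without a power calculation or an assumed SD. The assay list has 18 analytes. The only reference to incomplete participation in two visits is a payment rule under Briefing session and informed consent: "Participants who wish to withdraw after completing the first study visit will be reimbursed".

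**The concern.** What is randomised is the order of the two forms, so the difference in change between capsule and beverage is the contrast that the crossover serves. The change from fasting to 1 hour within a form is an uncontrolled before-after comparison. The plan attaches intervals to the uncontrolled quantity and names only a test for the randomised one.

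A report could follow the wording and give, for each analyte, two within-form intervals and a p-value. The two intervals would not show how precisely the difference is known, because they carry no information on the correlation between a person's two visits. With only 15 participants this could mislead. A paired test that just misses significance is compatible with differences from zero to about 1.11 SD of the paired differences (twice the half-width of 0.554), and a bare p-value might be taken to mean that the forms are interchangeable.

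**Working it through.** **Inputs.** From the documents: n = 15, each participant taking both forms, a 95% level and a paired t-test. The sample size has no stated derivation, so there is no planned figure to reproduce. Assumed, because the documents give no values: equal SD of the change for both forms (used as the unit), between-visit correlation r of 0, 0.5, 0.8 or 0.9, and mean changes of 1.5 and 1.0 for the two forms.

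**Step 1: within-form intervals.** The half-width is t(0.975, 14)/√15 = 2.1448/3.873 = 0.554 SD, whatever r is. The two intervals in the example are 0.95 to 2.05 and 0.45 to 1.55.

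**Step 2: interval for the difference.** The SD of the paired difference is √(2(1 − r)), the standard error (SE) is that divided by √15, and the half-width is 2.1448 × SE. The mean difference is 1.5 − 1.0 = 0.5, and the paired t statistic is 0.5/SE on 14 degrees of freedom.

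| r | SE | Half-width | 95% CI for the difference | t | p |
|---|---|---|---|---|---|
| 0 | 0.365 | 0.783 | −0.28 to 1.28 | 1.37 | 0.192 |
| 0.5 | 0.258 | 0.554 | −0.05 to 1.05 | 1.94 | 0.073 |
| 0.8 | 0.163 | 0.350 | 0.15 to 0.85 | 3.06 | 0.008 |
| 0.9 | 0.115 | 0.248 | 0.25 to 0.75 | 4.33 | 0.0007 |

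The half-width varies by a factor of 0.783/0.248 = 3.2 while the within-form intervals stay fixed. The concern is right that those intervals alone do not give the precision of the difference.

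**Step 3: bring in the p-value the plan also produces.** The p-value on 14 degrees of freedom gives |t|. Subtracting the two reported means gives d = 0.5. Then SE = |d|/|t|, and the interval is d ± 2.1448 × SE. Starting from the rounded p-values:

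- p = 0.192: |t| = 1.371, SE = 0.365, CI −0.28 to 1.28.
- p = 0.073: |t| = 1.938, SE = 0.258, CI −0.05 to 1.05.
- p = 0.008: |t| = 3.089, SE = 0.162, CI 0.15 to 0.85.
- p = 0.0007: |t| = 4.324, SE = 0.116, CI 0.25 to 0.75.

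These match Step 2 to two decimals. The p-value carries the correlation that the within-form intervals lack.

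**Step 4: what would differ if the interval were written into the plan.** The paired test and the 95% interval use the same differences, standard error and degrees of freedom, and the interval excludes zero exactly when two-sided p < 0.05. The estimate, test, error rate, power and data collected would all be the same.

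**The case for a change.** The strongest reply is that a plan should say what will be reported for its main comparison, and that back-calculation is a poor substitute. Recovery fails if p-values appear only as thresholds, is unstable if the observed difference is close to zero, and fails if the two means rest on different participants. The plan promises neither exact p-values nor means on the same complete pairs, and its payment rule allows for someone leaving after the first visit. Its authors also specified intervals for the first analysis, so leaving them out of the second is noticeable.

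Those limits are real, and they are why an explicit interval is the better way to report. They do not make the plan unsound. Each depends on a reporting choice or an event that the plan does not call for. The payment rule says what a withdrawing participant receives; it is not an expected dropout rate, and every participant is meant to complete both visits. Which participants enter the within-form means is a separate question from whether an interval is named.

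It can also be argued that the title, "The acute effect of instant coffee in different forms on plasma metabolites", makes the form difference the central question. It can equally be read as the acute effect of each form, for which intervals are promised. No primary endpoint is designated, so the emphasis on the contrast rests on the randomised order, which does support it.

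**Conclusion.** No change to the plan is needed. It is true that the text commits to 95% intervals only for the within-form changes and names only a paired t-test for the difference between forms. The test is valid, nothing precludes an interval, and an analyst running it has the mean difference and its interval to hand. Following the plan as written gives a sound result.

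The size of the matter is one unlisted output for each of 18 analytes. The 3.2-fold spread in half-width (0.78 to 0.25 SD) shows what the within-form intervals leave out under assumed correlations and equal SDs; it does not measure an error in the planned analysis. That the interval can be recovered rests on complete pairs, exact p-values and a difference not close to zero. Giving the mean paired difference, its interval and the number of pairs beside each p-value is sensible practice when the results are written up.

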Products, Nutrition and Allergies. Scientific Opinion on the safety of caffeine. EFSA J. 2015;13:4102.). The capsule used will be gelatin capsules that are purchased from NTUC FairPrice online. The brand is Now Foods. While the capsules are bovine sourced gelatin, it is not certified Halal or Kosher. The product empty capsules are produced under GMP (<https://www.nowfoods.com/now/about-now/seals-certifications/gmp>).

Sample processing and extraction

Blood will be collected in 4 Vacutainer® serum tubes (6mL each) and allowed to clot/stand at room temperature. After 30-40 min, serum will be separated from entire blood by centrifugation (2000g, 10 min, 24°C) and aliquoted into 1.5mL tubes. The remaining portion of samples that are left after serums have been separated from the samples will be discarded immediately after separation. All samples will be processed on the same day that they are collected. Samples will be stored at -80°C until all samples have been collected at the end of the intervention study and processed in a single batch. Briefly, thawed samples will be added with deuterated internal standards (for measure of control for extraction). Serum samples will be de-proteinised with acidified methanol, centrifuged (4000g, 10 min, 4°C) [15] and transferred into glass vials.

After collection of the blood samples at NUS, they will be transported to the NTU laboratory for measurements. Remaining samples may be stored NUS Saw Swee Hock School of Public Health Tissue Repository for up to 10 years for future measurements that are related to biomarkers of coffee intake and biomarkers related to its potential health effects, with the approval from the ethics board.

Targeted and untargeted metabolomic profiling

Serum samples will undergo targeted metabolomic profiling at the Singapore Phenome Centre located at NTU, which has state-of-the-art mass spectrometers and strong technical support. Targeted detection and quantification of a list of previously proposed coffee biomarkers (see metabolite assay list below) will be conducted on the serum samples using a Waters Acquity UHPLC-TQ-MS, and commercially available standards and deuterated standards. For atracyligenin, its lack of standard previously limited its detection but we have successfully synthesised this compound from its atracyloside

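### Unadjusted between-form paired t-tests on 18 listed analytes, with no primary analyte, multiplicity adjustment or exploratory label, leave an isolated p below 0.05 without a stated reading

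*Combined protocol and SAP*

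**What the plan says.** The analysis plan is two sentences under Statistical analysis. The first is estimation within each form: "We will calculate mean changes in serum concentrations of biomarkers between the fasting state and after ingestion of the capsule or coffee", with 95% confidence intervals. The second is the only between-form analysis: "we will test whether changes in concentrations differ between the coffee and the capsule intervention using paired t-tests".

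The analytes are set out just above. The metabolomic profiling section promises "Targeted detection and quantification of a list of previously proposed coffee biomarkers (see metabolite assay list below", and the Metabolite assay list runs from item 1 (atractyligenin) to its last entry, printed as "18,1,7-dimethyluric acid", that is, item 18. All entries have equal standing.

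Under Study Visit and Blood Collection, participants attend two visits "with random assignment to either coffee capsules first or coffee as a beverage first". Capsule versus beverage is therefore the trial's only randomised contrast. The planned size is given under recruitment: "Study participants (n=15) will be recruited via flyers".

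Nowhere do the documents name a primary analyte, a significance level for the t-tests, an adjustment for multiple testing, or an exploratory status for the comparisons.

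**The concern.** With 18 tests at a conventional 5%, the expected number of false positives when form makes no difference is 18 × 0.05 = 0.9, whatever the correlation between analytes. One analyte falling below 0.05 is thus an unremarkable result under no effect. The plan does not say whether such a result would be reported as a difference between capsule and beverage, or that all 18 results will be shown.

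What is at stake is the interpretation of the trial's one randomised comparison. The estimates themselves are not biased by this. The planned 95% confidence intervals do not help, because they are for the change from fasting within each form. The plan does not promise an interval for the between-form difference.

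**Working it through.** The plan states no error rate or power, so there is no figure of its own to reproduce.

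**Inputs**
- Number of tests m = 18 (Metabolite assay list).
- Pairs n = 15, hence 14 degrees of freedom if all complete both visits (Recruitment of study participants).
- Two-sided 5% per test: assumed.
- Correlation between the analytes' between-form differences: not given, so a range of common correlations is used.
- Normal paired differences: assumed, then relaxed.

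**1. Independent analytes, no true difference.** P(at least one false positive) = 1 − 0.95^18 = 1 − 0.397 = 0.603.

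**2. Correlated analytes.** Simulated sets of 18 paired t-tests, n = 15, normal differences, no true difference (200,000 sets per correlation; 40,000 at 0.99):

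| Common correlation | Any false positive |
|---|---|
| 0 | 60% |
| 0.3 | 52% |
| 0.5 | 42% |
| 0.7 | 29% |
| 0.9 | 16% |
| 0.95 | 12% |
| 0.99 | 8% |

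The rate falls to 5% only at correlation 1. At 0.9 it is still 0.16/0.05, about three times the per-test level.

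**3. Non-normal concentrations.** The plan tests changes in concentration and states no transformation. Taking each paired difference as a difference between two lognormal values, with independent analytes, gives about 57%, 48–49% and 35% for assumed log-SDs of 0.5, 1 and 1.5, because the t-test is conservative with such tails. At log-SD 1 with log-scale correlation 0.5 or 0.9 it is 35% or 14%.

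**4. Uneven correlation.** With nine analytes correlated at 0.9 and nine independent (normal), the rate is 45%.

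**5. Fewer quantifiable analytes.** If independent: 1 − 0.95^15 = 0.54, 1 − 0.95^12 = 0.46, 1 − 0.95^9 = 0.37. At correlation 0.9 the simulated values for 15, 12 and 9 analytes are 15%, 14% and 13%.

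**6. What adjustment does.**
- When nothing differs, Benjamini-Hochberg over 18 tests brings the chance of any false positive to 2.5–5% over the correlations simulated.
- Once some analytes differ, it controls the false discovery rate (at most 4.7% in these runs). It does not control the chance of any false positive, which was roughly 7–22% when nine differed by 1.2 SD.

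**7. What a binding adjusted threshold would cost.** Effects are in SDs of the within-person between-form difference.
- Unadjusted power at 0.8 SD with n = 15 (noncentrality 0.8 × √15 = 3.10) is 82%.
- Requiring a Benjamini-Hochberg p of at most 0.05 gives 35–37% per analyte if 1 of 18 truly differs, 46–47% if 3, 53–54% if 5 and 63–66% if 9.
- At the Bonferroni bound, 0.05/18 = 0.0028, power is 35%, and the difference detectable with 80% power rises from 0.78 to 1.18 SD.

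**The case against.** The strongest reply is that this is a 15-person, single-dose, one-hour study of candidate biomarkers, with no stated significance level or decision rule. Such work is commonly read as exploratory, and if all p-values are published anyone can adjust them later. Much of that stands, and it is why the point is modest. But the plan neither calls itself exploratory nor undertakes to report every analyte, so both safeguards depend on decisions made after results are seen.

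A second reply is that 60% overstates the problem. That also stands: the figure needs independence and near-normal differences. Several listed analytes are caffeine and related methylxanthines, so some correlation is plausible, though the documents do not quantify it.

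Three stronger readings are tempting and should be resisted:
- A reader might infer that the family of tests is undefined, because a section heading reads "Targeted and untargeted metabolomic profiling". The text beneath says "Serum samples will undergo targeted metabolomic profiling" and points to the list, and no untargeted analysis is described. The family is the 18 listed analytes; the heading merely needs tidying.
- A reader might infer that the trial will probably report a false difference. The documents state no rule by which a single small p-value becomes a claim, so the figures describe the tests and not a planned conclusion.
- A reader might infer that formal adjustment or a primary analyte is required. Nothing in the documents commits the trial to a confirmatory claim, and a binding threshold at n = 15 is costly.

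**Conclusion.** The point holds and is one to consider. As written, the plan produces 18 unadjusted between-form p-values with no rule for reading them, and these cannot support an isolated claim that form matters. Under two-sided 5% tests, 15 complete pairs, normal differences and no true difference, the chance of at least one false positive is about 60% with independent analytes, 42% at common correlation 0.5 and 16% at 0.9. With independent but heavy-tailed concentrations it is about 35–57%. Sixty per cent is therefore the upper end, and 16% is not a floor. The level, correlation and distribution are all assumptions. That no primary analyte, adjustment or label is given can be read directly from the plan and depends on none of them.

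**What to change.** Add to Statistical analysis, before the stored samples are assayed:

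> For every analyte on the assay list that can be quantified (decided before the forms are compared), we will report the mean between-form difference in change with its 95% confidence interval, the unadjusted paired t-test p-value and a Benjamini-Hochberg adjusted p-value across these analytes. All between-form results, adjusted and unadjusted, are exploratory, and an unadjusted p-value below 0.05 alone will not be described as a difference between forms.

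The exploratory label must cover the adjusted p-values too; otherwise they would be reported with no rule for reading them. Because the samples are held and assayed together after collection ends, the wording can be fixed before any result exists.

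The cost is a little more analysis work and more cautious between-form claims. No new data are needed and nothing already planned is removed.

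Three further steps are optional trade-offs. Restricting claims to an adjusted p of at most 0.05 cuts power at 0.8 SD from 82% to about 35–66%, depending on how many analytes truly differ. Holm holds the chance of any false positive at 5% even when some analytes differ, with power of about 35–36% (1 differs) to 38–39% (9 differ). Naming one primary analyte keeps 82% for that analyte only.

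### Order is randomised over two visits, but the only between-form test is a paired t-test with no visit term; adding one is a cheap improvement, not the repair of an error

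*Combined protocol and SAP*

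**What the plan says.** Under Study Visit and Blood Collection, each participant attends two visits, 7 to 28 days apart, and receives both forms, "with random assignment to either coffee capsules first or coffee as a beverage first". On balance it says: "The number of participants randomised to start with the capsule will be similar to those starting with the beverage". Blood is drawn at each visit "at fasting and 1 hour after the consumption of the coffee capsule/drink", so the outcome is a change from that visit's own fasting sample.

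The Statistical analysis section has two sentences. The first promises mean changes with 95% confidence intervals. The second is the only between-form comparison: "we will test whether changes in concentrations differ between the coffee and the capsule intervention using paired t-tests". No period, visit, order or sequence term and no mixed model appears in the document.

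Two other places bear on the point. Recruitment of study participants sets n at 15, without a derivation. Briefing session and informed consent foresees loss after the first visit ("Participants who wish to withdraw after completing the first study visit will be reimbursed" a partial sum) but gives no expected rate.

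**The concern.** The design randomises order, yet the test ignores it. A shift in level that affects the fasting and one-hour samples of a visit alike cancels in the change score. A shift in the one-hour response itself does not cancel. It pushes the beverage-minus-capsule difference up in one order group and down in the other.

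The paired t-test pools the two groups, so this systematic gap inflates its variance estimate. Near balance the price is a wider interval and lower power. If the orders are unequal among completers, part of the shift also enters the estimate as bias, and in sufficiently uneven splits the type I error rises above 5%. This is the trial's only comparison of the two forms, and it is applied to each of 18 listed analytes in 15 people.

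**Working it through.** **Inputs from the document.** n=15; two visits with randomised order; similar numbers in each order (closest split 8/7); outcome is the change from fasting to one hour; paired t-test. A two-sided 5% level is inferred from the 95% intervals.

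**Nothing to reproduce.** No SD, effect size or power accompanies n=15, so results are in units of the residual SD of the between-form difference.

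**Assumptions made here.** P, the visit-2 minus visit-1 shift in the one-hour response, is varied from 0 to 1 in the power comparison. T=0.778 is the effect that gives the paired t-test 80% power at n=15 when P=0. Errors are normal and there is no carry-over.

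**Model.** With D the beverage-minus-capsule difference in change:

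- capsule first (n1 people): D = T + P + e
- beverage first (n2 people): D = T - P + e, with e ~ N(0,1) and N = n1 + n2

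**Planned test.** The mean of D is N(T + P(n1-n2)/N, 1/N). It is independent of (N-1)s², which is noncentral chi-square on N-1 df with noncentrality 4P²n1n2/N. At 8/7 the noncentrality is 4×56/15 × P² = 14.93P², so E[s²] = 1 + 14.93P²/14 = 1 + 1.067P². At |P|=0.5 the inflated SD is √1.267 = 1.125. Rejection rates come from numerical integration over this distribution.

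**Adjusted test.** The estimate is the average of the two order-group means, with SE 0.5√(1/n1+1/n2) and N-2 df. At 8/7 the SE is 0.5√(1/8+1/7) = 0.2588, against 1/√15 = 0.2582 for the paired test. The critical value moves from 2.145 to 2.160. Power is 79.4% whatever the value of P.

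Results at 8/7 (width ratio is the mean paired interval over the mean adjusted interval):

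| Size of P | Width ratio | Paired type I error | Paired power, P positive / negative | Average | Points lost v. 79.4% |
|---|---|---|---|---|---|
| 0 | 0.992 | 5.0% | 80.0% | 80.0% | -0.6 |
| 0.25 | 1.025 | 4.4% | 79.8% / 76.3% | 78.0% | 1.3 |
| 0.5 | 1.117 | 3.1% | 75.9% / 68.0% | 72.0% | 7.4 |
| 1 | 1.433 | 0.8% | 58.2% / 39.9% | 49.0% | 30.4 |

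The last row is extreme: a two-SD gap between order groups, with P larger than T.

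**Other splits.** Bias of the paired estimate is P(n1-n2)/N. Break-even is the size of P above which adjusting narrows the interval. Type I error is the maximum as the size of P runs from 0 to 3.

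| Split | Bias | Power points lost by adjusting if P=0 | Break-even | Maximum paired type I error |
|---|---|---|---|---|
| 8/7 | P/15 | 0.6 | 0.12 | 5.0% |
| 8/6 | P/7 | 1.4 | 0.18 | 5.0% |
| 9/6 | P/5 | 2.1 | 0.23 | 5.0% |
| 8/5 | 3P/13 | 3.0 | 0.27 | 5.0% |
| 8/4 | P/3 | 5.9 | 0.39 | 5.6% |
| 10/5 | P/3 | 5.3 | 0.38 | 6.9% |

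Simulation at 8/7, 9/6, 8/5 and 10/5 (200,000 trials per setting) agrees within 0.3 points.

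**How likely the uneven splits are.** Start from 8/7 and suppose withdrawal is unrelated to order. One withdrawal gives 8/6 with probability 7/15 = 46.7%. Two give 8/5 with probability (7×6)/(15×14) = 20.0%. Three give 8/4 with probability (7×6×5)/(15×14×13) = 7.7%.

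**The case against.** The planned test is a legitimate pre-specified analysis. With randomised order and similar group sizes, its type I error stays at or below 5%, so it errs only toward caution. The whole benefit of adjusting depends on P, and the document gives neither an estimate of P nor a mechanism for it.

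Much in the design argues against a large shift. Each change is measured from the same visit's fasting sample, and site and dose are the same at both visits. Participants fast overnight, follow 24-hour food restrictions and are told to "avoid vigorous physical activity except for activities of daily living for at least 24 hours prior to the session". Samples are held "until all samples have been collected at the end of the intervention study and processed in a single batch", which removes an assay difference between visits. At |P|=0.25 the loss is trivial; a material loss needs |P| near 0.5, a one-SD gap between order groups.

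The 7.4-point loss is also an average over the two signs of P. It is 3.4 points if the P/15 bias happens to favour the paired test and 11.3 if it does not. Finally, the visit term costs most in the uneven splits where bias and type I error are the worry.

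All of this stands, and it limits the size of the benefit. It does not remove the case for adjusting: the sign of P is unknown in advance, so the average is the fair summary, and near balance the possible loss is much larger than the cost of insuring against it. The type I argument is weak. It needs 10/5, which would conflict with the promise of similar numbers, or 8/4, which is unlikely. An 8/5 split does not exceed 5%.

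**Conclusion.** The point holds as a recommended improvement, with medium confidence. The paired t-test is not wrong, and if P is near zero it loses nothing. A visit shift of 0.5 residual SD would cost it about 7 points of power at 8/7; one of 0.25 would cost about 1 point. Adjustment also removes the bias from unequal orders at any split. Exact balance is impossible with 15 people, and withdrawals could widen the imbalance. These sizes rest on the assumed T and P, normal errors and no carry-over. The document supplies no SD or effect size with which to convert them to concentrations.

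**What to change.** Replace the paired t-test sentence with one along these lines: for each analyte, compute each participant's beverage-minus-capsule difference in change, regress it on order coded +1 (capsule first) or -1 (beverage first), and take the intercept with its 95% CI as the between-form estimate. The slope then estimates the visit shift. Specify this before the data are seen, so that the decision to adjust is not data-driven, and report the order split among completers.

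The change needs no new data and one degree of freedom. With no visit shift the interval widens by 0.8% at 8/7, 1.7% at 8/6, 2.7% at 9/6 and 3.6% at 8/5. Below the break-even for the realised split, the adjusted interval remains slightly the wider of the two.

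Secondary: if an 8/7 split is wanted, fix it in the allocation list, for example as a permuted list of 8 and 7. Blocking alone may not secure it. At n=15, blocks of 2 or 4 always give 8/7, but blocks of 6 give 9/6 with probability 2/C(6,3) = 2/20 = 10%.
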